# **Protocol Details**

**Basic Info** 

Confirmation Number: deiffibj Protocol Number: 849894

Created By: [name] Principal Investigator: **[name]** 

Protocol Title: Investigating how Incentives Impact Engagement with an Online Mental Health Application (Neuroflow)

Short Title: **Neuroflow App Wellbeing Study** 

Protocol Description: The primary research goal of the proposed project is to understand how incentives (either points

> alone or points that can be exchanged for gift certificates) encourage engagement with an online mental health app, Neuroflow, for college students at the University of Pennsylvania. The

secondary aim is to compare participant outcomes across the groups of participants.

Application Type: **EXEMPT Category 3** 

### Resubmission\*

Yes

#### **Hospital Sites**

Will any research activities and/or services be conducted at a Penn Medicine affiliated hospital site?

### Other Investigator

None

# $Responsible \ Org \ (Department/School/Division):$

4412 - PS-Psychiatry

# Disclosure of Significant Financial Interests\*

Does any person who is responsible for the design, conduct, or reporting of this research protocol have a **FINANCIAL INTEREST**?

No

### Penn Intellectual Property\*

To the best of the Principal Investigator's knowledge, does this protocol involve the testing, development or evaluation of a drug, device, product, or other type of intellectual property (IP) that is owned by or assigned to the University of Pennsylvania? Please refer to the Patent and Tangible Research Property Policies and Procedures.

No

#### Certification

I have reviewed the Financial Disclosure and Presumptively Prohibited Conflicts for Faculty Participating in Clinical Trials and the Financial Disclosure Policy for Research and Sponsored Projects with all persons who are responsible for the design, conduct, or reporting of this research; and all required Disclosures have been attached to this application.

Yes

### The following documents are currently attached to this item:

There are no documents attached for this item.

# **HRPP**

#### **Human Source Material\***

Does this research include collection or use of human source material (i.e., human blood, blood products, tissues or body fluids)? IF YES, consult the EHRS web site: www.ehrs.upenn.edu/programs/bio/bbpathogens.html for information on OSHA Bloodborne Pathogens requirements (training, vaccination, work practices and Exposure Control Plan). If you have questions, call [contact].

# Image Guided Biopsies\*

Does the research involve imaging guided biopsy? IF YES, please contact the Clinical Imaging Core.

See https://www.med.upenn.edu/cbi for more details. Any questions should be directed to the Director of Research Operations, Dept of Radiology, [name].

No

### **HIPAA / Protected Health Information**

Does the research proposal involve accessing (viewing / using), collecting, or disclosing of protected health information (PHI) directly from participants or their medical or dental record for research purposes?

No

#### **HIPAA / Protected Health Information**

Does the research proposal involve accessing (viewing / using), collecting, or disclosing of protected health information (PHI) directly from participants or their medical or dental record for research purposes?

No

### **Remote Study Visits**

Does the research proposal involve conducting research visits remotely via any type of video conferencing software?

No

### **Remote Study Visits**

Does the research proposal involve conducting research visits remotely via any type of video conferencing software?

No

#### **CHPS Resources\***

Does the research involve CHPS resources?

No

#### **HUP Inpatient Nursing Resources**

Does this research include an inpatient admission at HUP?

No

# Pathology and Laboratory Medicine Resources\*

Will samples be collected by hospital phlebotomy and/or processed or analyzed by any of the clinical laboratories of the University of Pennsylvania Health System?

No

# Research Involves Apheresis, Cell Collection, and/or Blood Product Collection\*

Does this research involve collection of blood products in the Penn Donor Center and/or the use of apheresis for treatment or collection of cells or other blood components?

No

## Research involving blood transfusion or drug infusions\*

Will your research involve blood transfusion or infusion of study drug in 3 Ravdin Apheresis Unit for research purposes?

No

# **HUP Perioperative and Procedural Services \***

Does the research require the following: The collection of tissue, fluid, or blood in HUP Perioperative and Procedural Services ORThe administration of medications in HUP Perioperative and Procedural Services? This is inclusive to all phases of Perioperative care: pre-operative, intraoperative, and postoperative periods in all HUP Perioperative Procedure locations. If you have questions, please contact: [contact]

N/A

#### **Trial in Radiation Oncology**

Is this research a prospective trial being done in Radiation Oncology, and if so, has this protocol been approved by the Radiation Oncology Protocol committee?

N/A

### **Study in Radiation Oncology**

Is this research a retrospective study being done in Radiation Oncology, and if so, has this project been reviewed by the Radiation Oncology Clinical Research Group?

N/A

#### Use of UPHS services\*

Does your study require the use of University of Pennsylvania Health System (UPHS) services, tests or procedures, whether considered routine care or strictly for research purposes? (UPHS includes all Penn hospitals and clinical practices, including the Clinical Care Associates network of community practices). Examples of UPHS services/tests/procedures includes the Clinical Translational Research Center (CTRC), laboratory tests, use of the pathology lab, cardiovascular imaging tests or radiology imaging tests (whether being billed via the Service Center or through UPHS), other diagnostic tests & procedures and associated professional services, etc.

#### Veteran's Affairs (VA) Patients or Subjects

Does your study involve data from Veteran's Affairs (VA) patients or subjects? No

# If yes, was this approved by the Philadelphia VA?

No

#### **Out of State Research**

Will any Penn personnel conduct any research activities outside of the State of Pennsylvania? No

### Research involving Virtua Health

Will any Penn personnel conduct any research activities at a Virtua Health site location, OR in collaboration with Virtua Health System personnel, OR using any Virtua Health System resources (e.g., medical records)?

No

## **Primary Focus\***

Clinical Trial (prospectively assigning subjects to health-related interventions to evaluate outcomes)

#### **Protocol Interventions**

x Sociobehavioral (i.e. cognitive or behavioral therapy)

Drug

x Device - therapeutic

Device - diagnostic (assessing a device for sensitivity or specificity in disease diagnosis)

Surgical

Diagnostic test/procedure (research-related diagnostic test or procedure)

Obtaining human tissue for basic research or biospecimen bank

x Survey instrument

None of the above

### The following documents are currently attached to this item:

There are no documents attached for this item.

# Department budget code

000 - 000 - 0 - 000000 - 0000 - 0000 - 0000

# **Funding Sponsors**

### Funding sponsors billing address

If you have selected a commercial or industry sponsor, please provide the appropriate address and contact information for the Sponsor for the purposes of billing for IRB review fees (initial review, continuing review and convened modification fees apply here). If the Sponsor is not industry/commercial, this information is not necessary to provide with your application.

# **Funding sponsors gift**

Is this research being funded by a philanthropic gift?

## **Project Funding\***

Is this project funded by or associated with a grant or contract?

### **Sponsor Funding**

Is this study funded by an industry sponsor?

#### Status of contract

# The following documents are currently attached to this item:

There are no documents attached for this item.

# **Protocol**

# **Objectives**

#### Overall objectives

Primary: Differences in user engagement and retention over four weeks (28 days) by two forms of behavior economics incentives (either with its usual system of point incentives or with financial incentives). User engagement will be measured by the number of active users, the number of activities completed, and completion of daily mood and sleep ratings. Secondary: Differences in user anxiety, depression, well-being and emotion regulation levels after engagement with the NeuroFlow app, and how it varies by the incentives used for app engagement.

### **Background**

As mental health awareness and intervention has gained more traction throughout the years, applications - such as NeuroFlow - have emerged in an effort to facilitate aid to those who are unable to afford or access alternative mental health care methods (Huckvale et al, 2020). However, over 95% of mental health and wellness applications have not actually been studied (Lecomte et al., 2020).

Additionally, a large portion examines user adoption of various mental health applications based on different factors, leaving a gap in research regarding client engagement and interest post-installation (Huang and Bashir, 2017). Thus, despite promises, applications for promoting mental health often do not achieve their intended goals due to lack of sufficient client engagement/interest. In order to address this discrepancy, the use of financial incentives and other incentives from the field of behavioral economics may help (Beidas et al., 2019). As an application, NeuroFlow embeds behavioral economic principles to increase motivation and engagement with the application (such as personalized pop-up notification reminders and app gamification including points accrual for activity completion and celebratory messages for meeting points thresholds) and also provides financial incentives whereby points accrued can be redeemed into gift cards for popular outlets such as Amazon. However, it is not clear if this financial incentive increases engagement or has knock-on effects for mental health and wellbeing over and above the behavioral economics incentives per se. In this study, we will conduct a pilot two-arm randomized controlled trial where we will examine the effect of a treatment group (NeuroFlow app with behavioral economics and financial incentives vs. NeuroFlow app with behavioral economics incentives only) on application engagement and mental health and wellbeing (anxiety and depression symptoms, sleep, self-regulation and wellbeing). The purpose of this study is to gain an understanding of how incentives encourage participation and engagement with an online mental health platform, NeuroFlow.

# Study Design

### Design

This is a two-arm randomized controlled trial assessing the impact of various incentives (points or monetary) on user engagement and retention on the mobile mental health platform, Neuroflow. This study will utilize a block randomization procedure to assign subjects to one of two treatment groups and a between-subjects design in order to understand how the different incentives impact user engagement with the platform. After consenting to participate in the study, participants will be asked to complete the NeuroFlow daily check in for 28 consecutive days, incentivized by either points only, or points redeemable for gift cards (monetary incentive).

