### Participant recruitment

Please describe the plan to equitably identify and recruit a diverse group of participants that is reflective of the population under study. If this is a multicenter protocol, the recruitment plan should describe the local (Penn) site's plan. Describe:how potential participants may be identified (review of medical records, Slicer Dicer, DAC reports including referrals from physician offices and clinics);who may approach potential participants;methods to achieve sample diversity and inclusiveness;what information may be presented to or discussed with them; andthe context and setting in which recruitment will happen.

Subjects will primarily be recruited from the University of Pennsylvania through the online participant study pool, SONA. Individuals will receive a link to a web-based form after signing up where they will give their consent to participate in the study. If participant recruitment through SONA is insufficient to meet our target sample size, we will additionally recruit other University students from the United States through class email lists, social media platforms (e.g., Facebook class groups), and flyers (with a scannable barcode and detablable pieces with contract information) around campus. No participants under the age of 18 will be enrolled.

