# The following documents are currently attached to this item:

There are no documents attached for this item.

If there is subject compensation, provide the schedule for compensation per study visit or session and total amount for entire participation, either as text or separate document

There will be no financial compensation for participation in this study. For students enrolled at the University of Pennsylvania who registered through the SONA system, 4 credits will be awarded after the completion of the study and prior to the end of the semester. Additionally, participants will not be compensated for enrollment in the study but if randomized to the controlled group they will be able to cash in accrued points received for completing app activities for gift cards(maximum points = 1000 per month =  $\sim$ \$10).

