### **Analysis Plan**

The anticipated statistical analyses to be conducted for this study is a Linear-mixed effects model (LMMs). These models will be used to examine the effect of different incentives (behavioral economics and financial vs. behavioral economics only) on user engagement (measured by the number of active users, the number of activities completed, and completion of daily mood and sleep ratings) and retention. We will also examine the effect of incentive type on secondary mental health outcomes such as anxiety symptoms (GAD-7total score), depression symptoms (PHQ-9 total score), wellbeing (WHO-5total score)and emotion regulation (DERS total score).

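### If the fallback recruitment route is opened, recruitment source (4 SONA credits versus none) is neither a blocking stratum nor a model term, at a modest cost in precision

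*Combined protocol and SAP*

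**What the plan says.** **Randomisation.** The Design section says: "This study will utilize a block randomization procedure to assign subjects to one of two treatment groups". It gives no stratification factor, block size or allocation ratio.

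**Analysis.** The Analysis Plan says: "The anticipated statistical analyses to be conducted for this study is a Linear-mixed effects model (LMMs"). On content it says: "These models will be used to examine the effect of different incentives (behavioral economics and financial vs. behavioral economics only) on user engagement". It lists no covariates, and recruitment source does not appear.

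**Recruitment.** Participant recruitment says: "Subjects will primarily be recruited from the University of Pennsylvania through the online participant study pool, SONA". The second route is conditional: "If participant recruitment through SONA is insufficient to meet our target sample size, we will additionally recruit other University students from the United States". The means are class email lists, social media and flyers. The expected split between routes is not given.

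**Reward.** Under Subject compensation: "For students enrolled at the University of Pennsylvania who registered through the SONA system, 4 credits will be awarded", after completion and before the semester ends. Participation is otherwise uncompensated. The gift cards, worth at most about $10 a month, depend on arm and not on recruitment route.

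**The concern.** The primary objective is engagement and retention over 28 days, and the trial's premise is that rewards move both. The credits are an extra reward that one recruitment source has and the other lacks. The trial's own monetary contrast is only about $10 a month, so a 4-credit difference cannot be assumed trivial beside it.

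If both sources end up in the sample, part of the spread in engagement may be a source difference. A model without source leaves that part in the residual variance, and blocks that ignore source let its share differ between arms by chance. Both consequences are avoidable, because source is known before randomisation. Deciding whether to adjust only after seeing the data would also leave an analyst's choice open that could be closed now.

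**Working it through.** **The plan's own figure.** Enrolment is 100 (Subjects enrolled by Penn Researchers). It cannot be reproduced, because the documents give no alpha, power, effect size, SD or dropout. For orientation, with 50 per arm and two-sided alpha 0.05, the difference detectable with 80% power is (1.960 + 0.842) × √(2/50) = 0.560 SD.

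**Assumed inputs.** None of these is in the documents:
- 1:1 allocation, 50 per arm, two-sided alpha 0.05, no dropout;
- d = 0.5 in units of the unadjusted SD;
- non-SONA share p = 0.1 to 0.3, with 0 and 0.5 as the ends of the scale;
- engagement gap between sources g = 0.3 to 0.5 within-source SD, with 1.0 as the extreme.

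A two-sample t-test on one engagement score per person stands in for the mixed model.

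**Step 1: variance due to source.** With within-source variance 1, total variance is V = 1 + p(1−p)g². Source explains R² = 1 − 1/V.

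**Step 2: power.** Unadjusted power at d = 0.5 is 0.697. Adjusting raises the standardised effect to 0.5 × √V. The one degree of freedom spent is ignored.

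| p | g | V | R² | Adjusted d | Adjusted power |
|---|---|---|---|---|---|
| 0 | any | 1.000 | 0% | 0.500 | 0.697 |
| 0.1 | 0.3 | 1.008 | 0.8% | 0.502 | 0.700 |
| 0.2 | 0.5 | 1.040 | 3.8% | 0.510 | 0.714 |
| 0.3 | 0.5 | 1.053 | 5.0% | 0.513 | 0.719 |
| 0.5 | 1.0 | 1.250 | 20% | 0.559 | 0.790 |

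The gain is 0.3 to 2.2 points over the main range and about 9 points in the extreme case.

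**Step 3: the same question on another scale.** Fix the effect at 0.560 within-source SD, so that adjusted power is 0.80. Unadjusted power is then 0.797 (p = 0.1, g = 0.3), 0.780 (p = 0.3, g = 0.5) and 0.707 (p = 0.5, g = 1.0). The losses are 0.3, 2.0 and 9.3 points, so the choice of scale does not matter.

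**Step 4: chance imbalance.** If arrival order is mixed, the difference between arms in non-SONA share has SD 2√(p(1−p)/100). At p = 0.3 this is 2√(0.21/100) = 0.092, or 9.2 points. With g = 0.5 it moves the arm difference by 0.092 × 0.5 = 0.046 SD, a variance of 0.0021. The unadjusted variance of the arm difference is 4 × 1.0525/100 = 0.0421, which is 0.0400 + 0.0021. The imbalance is therefore exactly the extra variance already counted in Step 2, and not a second cost.

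**Step 5: how visible the imbalance would be.** In 20,000 simulated allocations with blocks of 4 (assumed), concurrent arrival and p = 0.3, the arms differed by 12 points or more in about 23% of trials. A 12-point difference shifts the estimate by 0.12 × 0.3 = 0.036 to 0.12 × 0.5 = 0.06 SD, or 0.12 SD at g = 1.0. The standard error is about 0.20 SD. If the sources arrive strictly one after the other, blocking over time holds the SD of the imbalance to about 2 points or less.

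**The case against.** The strongest reply is that the problem may never arise. The second route opens only if SONA falls short. If SONA supplies all 100 over the two semesters, source is constant and there is nothing to adjust for. This stands, and the point is conditional for that reason. The route is not remote, however: the target population includes other US universities, flyers and social media text are prepared, and Procedures and Consent are written for more than one recruitment method.

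A reader might infer that source is a known prognostic factor. The documents do not support that. No section says or measures that source predicts engagement. The credits follow completion of the study and are not tied to daily check-ins or activity counts, and Consent lets participants withdraw without consequences. A link is plausible on the trial's premise, but its size is assumed.

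A reader might also infer that the comparison is biased. It is not, because allocation is random and so independent of source.

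The largest figures need a 50% non-SONA share, which fits poorly with SONA as the main source.

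Finally, the Analysis Plan is one short paragraph that names no covariates at all. It is silent on source and does not rule it out. That is fair, but silence leaves the choice of covariates open until after the data are seen.

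**Conclusion.** The point holds in conditional form. If fallback recruitment is used, a factor that plausibly affects the primary outcomes is known at sign-up, yet neither the randomisation nor the model uses it. The consequence is lost precision only. It is at most about 2 power points for p = 0.1–0.3 and g = 0.3–0.5, about 9 points in the extreme case, and nothing if all participants come from SONA. These sizes rest entirely on the assumed share, gap and effect size. The documents do not support a claim of bias, or a claim that the trial as planned certainly mixes the two sources. Priority is low to moderate: the gain is small, but it is nearly free.

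**What to change.** 1. Record recruitment source at sign-up. Define it by SONA registration and not by university, because the credits follow SONA registration and flyers or social media may also bring in University of Pennsylvania students.
2. If the fallback route is opened, run the block randomisation from separate lists for SONA and non-SONA participants.
3. State in the Analysis Plan that source enters the engagement and retention models as a fixed effect whenever both sources are present, and drops out if only SONA is used. Blocking within source is not enough alone, because an unadjusted model still counts the source difference as error. In the symptom, well-being and emotion-regulation models the term is optional, since the argument concerns engagement.
4. Report arm effects by source descriptively only. At 20% non-SONA, that group would have about 10 people per arm.

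The cost is one recorded variable, a second list and one degree of freedom. If participants have already been randomised, the covariate alone can still be fixed before the usage metrics are pulled at the end of the study.

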#### **Study duration**

Participants will be actively in the study for approximately one month including four weeks (28 days) of app usage, with time to fill out the pre and post Qualtrics survey to examine changes in mental health related outcomes. Overall, participant recruitment for the study will span the Fall 2021 and Spring 2022 semesters.

# **Characteristics of the Study Population**

## **Target population**

The target population for this study are college students either at the University of Pennsylvania or other US universities. Participants will be included if they have a smartphone and are willing to download and use the Neuroflow app throughout the duration of the study.

# Subjects enrolled by Penn Researchers

100

# Subjects enrolled by Collaborating Researchers

0

# Vulnerable Populations

**Children Form** 

Pregnant women (if the study procedures may affect the condition of the pregnant woman or fetus) Form

Fetuses and/or Neonates Form

